### III. SUBJECT SELECTION

A total of 20 healthy adults (20-40 years old) will be studied in this proposal. In order to obtain 20 people who meet all the study criteria and complete the 33-day inpatient study, we expect to enroll up to 100 people in the screening process for the study. Based on similar studies in the past, we anticipate that up to 25 individuals may be enrolled in the main study in order to have 20 complete the study. Approximately equal numbers of men and women will complete the study in each group.

Each potential participant will undergo an extensive screening procedure prior to participation in the study. The procedure begins with a telephone/online screening (to determine general medical suitability) and answering any questions potential participants may have about the study. If the original preliminary telephone/online screening questionnaire reveals no grounds for exclusion (see below), then potential participants are asked to come for an interview and physical screening. The physical screening includes a medical history, blood and urine tests, an ECG, and a physical examination by a physician or other qualified personnel (i.e physician assistant, certified nurse practitioner). Participants will also undergo psychological screening (see below), including questionnaires and a structured interview with a clinical psychologist. Finally, participants will be screened for sleep apnea and periodic limb movement disorder using a home sleep test.

We estimate that up to 10 individuals will inquire about the study for every 1 eventually studied, and that up to 5 individuals will begin the screening process for every 1 who successfully completes the screening and begins the study. We therefore plan to enroll up to 100 participants in the study in order to have 20 who pass all the screening and complete the 33-day study.

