### Sample size and power calculation

We will consider three primary outcomes: insulin sensitivity for Specific Aim 1; glucose AUC for Specific Aim 2; and duration of melatonin secretion for Specific Aim 3. Sample size and power calculations are based on results from our previous studies. In the study of one week of sleep restriction to 5 h/night[13], we observed a ~28% decrease in insulin sensitivity as assessed by ivGTT. We anticipate a similar effect on insulin sensitivity in participants assigned to the Sleep Restriction with extended duration Artificial Light At Night (ALAN) group in the proposed study, given the identical conditions of 1 week of sleep restriction. In a separate study, no impairment of glucose tolerance was observed in a group of participants exposed to sleep restriction without extended duration exposure to ALAN (See Preliminary Studies, Fig. 3). With 20 subjects, we have 83% power ( $\alpha=0.05/3=0.0167$ , 2-sided paired t-test) to detect as little as a 13% difference between the conditions in the change from baseline (18% change with ALAN vs. 5% change without ALAN) in insulin sensitivity (assuming the common standard deviation (SD) of the change is 16%). This should be more than adequate to detect the difference in insulin sensitivity we expect to observe in the proposed study. For Specific Aim 2, with 20 subjects, we estimate that we have 83% power ( $\alpha=0.0167$ , 2-sided paired t-test) to detect as little as a 3.65% difference between the conditions in the change of glucose AUC (assuming common SD= 4.5%). This should be more than adequate to detect the difference in glucose AUC we expect to observe, given that we have previously observed an over 20% change in glucose AUC following a prior history of recurrent circadian disruption combined with chronic sleep restriction[32].

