For Specific Aim 3, we estimate that we will have 84% power ( $\alpha=0.0167$ , 2-sided paired t-test) with 20 subjects to detect a difference as small as 40 minutes (0.66 hrs) in the duration of melatonin secretion (1 hr with ALAN vs. 20 minutes without ALAN, assuming common SD=48 minutes). This should be more than adequate to detect the expected difference in melatonin secretion, given that we previously showed that evening exposure to room light shortened the duration of melatonin secretion by about 90 minutes (compared to dim lighting), even when participants remained in darkness for 8hrs/night during sleep[94]. Because participants in the current proposed

study will be exposed to room light for an extra 5 hrs/day in the sleep restriction with ALAN condition, we expect to see a more than 3-hour difference in the duration of melatonin secretion with and without ALAN.

For Exploratory Aim 4, we will consider two primary outcomes. We estimate that we have 85% power ( $\alpha=0.025$ , 2-sided paired-sample t-test) to detect an 20% difference in the change (25% with ALAN, SD=28% vs. 5% without ALAN, SD=6%) in levels of long-chain, highly unsaturated triglycerides, which have been associated with insulin sensitivity. Moreover, we estimate we will have 85% power to detect a difference as little as 11% in the change (5% with ALAN, SD=6% vs. 18% without ALAN, SD=19%) in levels of short-chain, highly saturated triglycerides, levels of which have been associated with increased diabetes risk.

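### Exploratory Aim 4 claims 85% power for an 11-point short-chain triglyceride difference, but the two means printed beside it differ by 13 points

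*Combined protocol and SAP*

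**What the plan says.** Section VI of the combined protocol and SAP, under Sample size and power calculation, names two outcomes for Exploratory Aim 4 and tests each at a two-sided alpha of 0.025 with a paired t-test.

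- **Long-chain, highly unsaturated triglycerides:** 85% power for a "20% difference in the change (25% with ALAN, SD=28% vs. 5% without ALAN, SD=6"%).
- **Short-chain, highly saturated triglycerides:** 85% power for a "difference as little as 11% in the change (5% with ALAN, SD=6% vs. 18% without ALAN, SD=19"%).

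The alpha and the test are printed in the long-chain sentence only. The sample size is not restated for this aim; section III says "A total of 20 healthy adults (20-40 years old) will be studied in this proposal". No correlation between a participant's two changes, and no SD of the paired difference, is given for either outcome.

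Two other power statements in the section print a pair of means. Aim 1 has a "13% difference between the conditions in the change from baseline (18% change with ALAN vs. 5% change without ALAN"), and Aim 3 has a 40-minute difference from "1 hr with ALAN vs. 20 minutes without ALAN".

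**The concern.** The detectable difference and the two means stand in one sentence and do not agree. All are whole percentages, so rounding does not explain a gap of 2 points. The text there is running prose with no redaction or table, so a reading error from the PDF is unlikely.

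At stake is what the plan tells a reader about its sensitivity on this outcome. If 11 is the wrong number, the plan claims to detect a smaller effect than its own inputs support. If a mean or an SD is wrong, the basis of the calculation is misreported. The plan treats this as one of two main outcomes of Aim 4 and splits alpha for it, so the statement should be reproducible from its own inputs.

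**Working it through.** **1. Subtraction, with no assumptions.**

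| Outcome | Printed means | Subtraction | Difference stated |
|---|---|---|---|
| Insulin sensitivity (Aim 1) | 18%, 5% | 13 | 13 |
| Melatonin duration (Aim 3) | 60 min, 20 min | 40 min | 40 min |
| Long-chain triglycerides (Aim 4) | 25%, 5% | 20 | 20 |
| Short-chain triglycerides (Aim 4) | 18%, 5% | **13** | **11** |

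Only the last row fails.

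**2. Inputs and formula for power.** n = 20 pairs (section III), and two-sided alpha 0.025 with a paired t-test (both from the long-chain sentence). Carrying n, alpha and the test over to the short-chain outcome is an assumption, though a natural one. The SDs are as printed. The correlation ρ is assumed, and a range is shown.

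SD_diff = √(s₁² + s₂² − 2ρs₁s₂). Power comes from the noncentral t distribution with 19 degrees of freedom and noncentrality d√20 / SD_diff.

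**3. Reproducing the plan's other figures.** For Aims 1 to 3 (alpha 0.0167), setting SD_diff equal to the printed common SD, which is what ρ = 0.5 implies, gives:

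- Aim 1 (13, SD 16): 83.2%, stated 83%.
- Aim 2 (3.65, SD 4.5): 83.0%, stated 83%.
- Aim 3 (0.66 h, SD 0.8 h): 84.4%, stated 84%.

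For the long-chain outcome at ρ = 0.5, SD_diff = √(784 + 36 − 168) = √652 = 25.53. Power for 20 points is 84.7%, stated 85%. The method and ρ = 0.5 therefore recover all four of these figures.

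**4. Short-chain outcome.** At ρ = 0.5, SD_diff = √(36 + 361 − 114) = √283 = 16.82.

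| Assumed ρ | SD_diff | Power at 11 | Power at 13 | Difference detectable with 85% power |
|---|---|---|---|---|
| 0 | 19.92 | 53% | 68% | 15.7 |
| 0.5 | 16.82 | 69% | 84% | 13.2 |
| 0.7 | 15.41 | 77% | 90% | 12.1 |

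A simulation of 200,000 trials at ρ = 0.5 gave 68.8% and 83.7%, against 68.7% and 83.7% from the formula.

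**5. Can one correlation serve both Aim 4 outcomes?** Ranges of ρ in which power rounds to 85%:

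- Long-chain, 20 points: 0.488 to 0.539.
- Short-chain, 13 points: 0.526 to 0.557. This overlaps the long-chain range at 0.526 to 0.539.
- Short-chain, 11 points: 0.871 to 0.894. There is no overlap; at ρ = 0.88 the long-chain power would be about 92%.

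**6. Could an SD be wrong instead?** For 85% at 11 points, SD_diff must be about 14.0. With the ALAN SD kept at 6%, the no-ALAN SD would have to be 12.6%, 16.0% or 17.5% for ρ = 0, 0.5 or 0.7, against 19% printed. These SDs are illustrative and are not in the plan.

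**The case against.** The strongest reply is that almost nothing follows from this. Aim 4 is exploratory, N = 20 is justified on Aims 1 to 3, and no analysis or decision uses the 11%. That is correct, and it caps the point at minor.

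A second reply is that the power argument borrows inputs that the sentence does not print. At a two-sided alpha of 0.05, 11 points would have 79% power at ρ = 0.5 and would reach 85% at ρ ≈ 0.68. But the plan splits alpha between the two outcomes, and at 0.05 the long-chain 85% would need ρ of about 0.06. Nor does any alpha change the subtraction.

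A third reply is that 13 should not be favoured. At exactly ρ = 0.5, 13 points gives 83.7%, which rounds to 84%, whereas 11 points with a no-ALAN SD of 16% gives 85%. This has force. That alternative needs two misprints (a mean and an SD) where a slip for 13 needs one, but the documents cannot settle it.

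A last possibility is that 11% is a relative difference: if both changes are increases, 1 − 1.05/1.18 = 11.0%. The wording speaks of a difference in the change, and the long-chain figure does not follow that rule. Read as the reductions that Aim 4 hypothesises, it would be 1 − 0.75/0.95 = 21%, not 20%. The reading is weak, and it too would need to be stated.

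**Conclusion.** The concern holds. The inconsistency is certain and needs no assumption: the printed means differ by 13 points and the plan states 11. At least one of the difference, means, SDs or power is wrong as printed, and the documents do not show which.

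The size of the power discrepancy is conditional. It rests on the printed SDs, 20 pairs, alpha 0.025 and an assumed correlation. At 0.5, the value that fits the section's other four power figures, power at 11 points is about 69% against 85% stated. Over correlations of 0 to 0.7 it is 53% to 77%, and only a correlation near 0.88 restores 85%. A slip for 13 is plausible but not proven. Severity is minor.

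**What to change.** Go back to the original calculation, reconcile the difference, means, SDs and power for the short-chain outcome, and state the correlation (or the SD of the paired difference), n and alpha used.

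- **If the printed means and SDs are right:** replace 11% with 13% and state about 84% power at an assumed correlation of 0.5. The 85% can stay if the correlation used was about 0.53 to 0.54.
- **If 11% is right:** correct the means, and the SDs if they are also wrong, and recompute. Power is about 69% at correlation 0.5 if the SDs of 6% and 19% stand. The 85% may be correct if the no-ALAN SD was misprinted too.

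While doing this, confirm the condition labels and the sign of the change. The short-chain sentence puts the larger change in the condition without ALAN, the reverse of the long-chain sentence, and gives no direction.

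The cost is wording and one restated figure. Sample size, design and analysis do not change.

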## **VII. Risks and Discomforts**

### **Potential Risks to Subjects Associated with Each Study Intervention, Procedure or Interaction.**

#### *Risks of blood sampling procedures.*

##### **Common Risks**

There may be some discomfort or bruising on initial insertion of the IV catheter into a vein but wearing the catheter should not be painful.

Occasionally, there is a black and blue mark at the site of the IV insertion, which may last a couple of weeks; and, rarely, a small scar may remain permanently at the venipuncture site.

Occasionally, mild discomfort may occur from the tube in the vein. If this happens, we will either reposition it or remove it entirely, asking the participant's permission before any subsequent reinsertion.

There may be a minor skin rash or reaction (contact dermatitis) to the sterile tape used to hold the catheter in position. Hypoallergenic tape will be used as necessary.

The amount of blood drawn should not significantly alter blood volume, although there may be a small decrease in the hemoglobin level. The total volume of blood drawn over the course of the month-long study will be no more than 2 pints (946 mL).

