Immediately after the ambulatory baseline, the participant will be admitted to the Center for Clinical Investigation (CCI) at BWH on Day 1. They will be scheduled to sleep for 10 hours overnight at the CCI (centered at their usual times), and their sleep will be recorded with standard polysomnography (PSG) on some or all of the nights. Upon awakening the next morning (Day 2), the participant will begin the **first Baseline Day**. They will be given isocaloric, nutrient-controlled meals (breakfast, lunch, dinner) and will be scheduled to sleep again for 10 hours overnight. This will continue for the remaining baseline days. Near the end of the first Baseline segment (approximately Day 5), they will have an IV catheter inserted into a forearm vein for blood sampling. After awakening the next morning (~Day 6) after an overnight fast, the participant will undergo an assessment of their resting metabolic rate via indirect calorimetry. This will be followed by a Mixed Meal Response at breakfast to evaluate their baseline glucose and insulin response to a meal (see below for details). Frequent blood samples for melatonin will also be drawn to assess the duration of melatonin secretion and melatonin levels during the metabolic assessments, and this sample collection will continue throughout the next three days (~Days 6-8). Upon awakening on Day 7 after an overnight fast, the participant will undergo an assessment of their resting metabolic rate via indirect calorimetry again, and this will be followed by a baseline insulin-modified IV glucose tolerance test (GTT) that will be carried out to assess insulin sensitivity ( $S_I$ ), acute insulin response (AIRg), and glucose effectiveness (see below). The IVGTT will be scheduled to begin at the same time as the Mixed Meal Response on the previous day. Sample collection for the IVGTT will be completed by approximately 3 hours later (4 hours after wake time). Beginning in the early afternoon, ambient lighting will be lowered to <15 lux and ~hourly blood samples for melatonin endogenous circadian rhythm assessment will be drawn. Sleep will be scheduled at the same time as Nights 1-6, and blood sampling will continue throughout the night. Sample collection for the circadian rhythm of melatonin will be completed by approximately 10 hours after wake time, at which time the sampling IV will be removed and the lighting will be returned to normal.

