For the **Washout**, sleep episodes will be scheduled to 10 hours each night at the same time of the Baseline sleep episodes, from Days 15-23. Upon awakening after an overnight fast toward the end of the Washout (~Day 23), the participant will undergo the second **Baseline** assessment of their resting metabolic rate, glucose and insulin responses, and melatonin rhythms. Standardized Mixed Meal Responses, ivGTTs, and melatonin sampling will be carried out on the next 3 days (~Days 23-25) as performed during the first Baseline assessment on Days 6-8. Following the washout, the next 7 nights are the **Second Sleep Intervention**, during which participants will undergo the sleep restriction condition (with or without ALAN) which they have not yet undergone during the first sleep intervention.

Upon awakening after an overnight fast at the end of the 7-day exposure (~Day 31), the participant will undergo another re-assessment of their resting metabolic rate, glucose and insulin responses, and melatonin rhythms. Standardized Mixed Meal Responses, ivGTTs, and melatonin sampling will be carried out on the next 3 days (~Days 31-33) as performed during the assessment following the first Sleep Intervention on Days 14-16. The final **Recovery** sleep episode on Night 32 will be scheduled for 10 hours at the same time of the Baseline sleep episodes. Blood sampling will be completed approximately 10 hours after waketime on Day 33, at which time the sampling IV will be removed and the participant will be discharged. At the times indicated above when blood sampling is scheduled, we may collect additional small amounts of blood to assay for proteins, lipids, transcripts, or metabolites.

**How Biospecimens, Data, and/or Records, will be Obtained.** As outlined above, activity/light data and diary recordings, as well as a blood sample for DNA extraction will be collected from participants during the pre-study screening period. In the laboratory study, PSG sleep and wake recordings, answers to written and computerized questionnaires, whole blood and saliva biospecimen will be collected. We may also collect breath samples and fecal samples during specific days of the study.

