**Standardized Mixed Meal Response test.** Post-prandial mixed meal metabolic responses will be assessed toward the end of each baseline and toward the end of each sleep intervention segment following the measurement of RMR/REE. This will be done after an overnight fast using a breakfast [32]. The meal will have the overall composition of the diet described above, but each participant will be served an identical breakfast at each test and will be required to eat all of the meal within 30 minutes. Blood samples (approximately 4mL) will be collected using the sample collection system described above, with careful attention to the timing of the start of the breakfast, and will include pre-meal baseline samples as well as post-prandial samples at ~10-min intervals for the first 90 minutes following the meal, then at ~30-min intervals for the next 90 minutes (total of 3 hours). The participant will remain sitting in bed until the final blood sample is drawn. The samples will be placed into collection tubes and centrifuged, then pipetted into small polystyrene tubes and stored at -80°C for later analysis of glucose, insulin, and other hormones using standard procedures and/or commercially available kits.

**Hormonal data.** The recording of the circadian rhythm of melatonin is essential, as it is considered a “gold standard” way to assess central circadian phase. The melatonin rhythm has been demonstrated to be the most precise and accurate marker of the human circadian pacemaker [98-100]. Samples of blood will be collected at approximately hourly intervals through the blood collection system described above. Blood samples (approximately 1-3mL) will be transferred to small (3 mL) vacutainer tubes and centrifuged; the resulting plasma will be pipetted into vials and frozen until analysis. Melatonin assays will be performed by Solidphase (Portland, ME) using a commercially-available radioimmunoassay kit.

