**Intravenous Glucose Tolerance Test (IVGTT; insulin-modified).** An insulin-modified IVGTT will be carried out on Days 7 and 15 after an overnight fast [13] and assessment of REE. Blood samples will be drawn via an intravenous catheter every 5 min for 20 min starting at T=-20 min. At time 0 (time of usual breakfast), 0.3 g/kg glucose will be administered over 1 minute as an intravenous bolus via an intravenous catheter in the opposite (non-sampling) arm. Blood samples will be taken at 2, 3, 4, 5, 6, 8, 10, 12, 14, 16, 19, 21, 22, 24, 26, 28, 30, 35, 40, 45, 50, 55, 60, 70, 80, 90, 100, 120, 140, 160, and 180 min. At time +20 min, 0.02U/kg human insulin will be administered intravenously over 1 minute. Minimal Model Analysis [102] will be used to assess insulin sensitivity ( $S_I$ ) and glucose effectiveness. Acute insulin response (AIRg) will be calculated as the average incremental plasma insulin concentration over the first 20 minutes after the glucose bolus (and before the insulin administration) [22].

**Continuous glucose monitoring.** As supplementary/exploratory data, we may use an Abbott FreeStyle continuous glucose monitor (Abbott Laboratories) to document glucose levels every 15 minutes throughout the inpatient study. If so, a physician or nurse will insert an interstitial glucose sensor in the participant’s arm on Day 4, and it will be replaced approximately every 10 days or as needed throughout the end of the study. The sensor will thus be worn throughout the study to collect continuous glucose data (one measurement every 15min). The data will be downloaded at the end of the collection period using a reader device. This information will provide a dynamic view of changes in glucose levels throughout the study, for example in near-darkness while awake.

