**Total fat mass and BMI**. Body Mass Index (BMI) will be assessed using measured height and weight, and waist and hip circumference. A DXA scan (Discovery W Dual-energy X-ray Absorptiometry Scanner, Hologic, Bedford MA) will be carried out at the BWH Bone Density and Body Composition Research Core to measure total fat mass prior to the start of the study and again at the end of the study. We will look for changes in fat mass, especially visceral/trunk adiposity, and will further be able to determine whether there are changes in muscle mass with the low levels of activity in controlled laboratory conditions.

**Saliva sample collection**. Saliva will be collected approximately every waking hour as a backup to the blood samples collected for melatonin [100]. Participants are instructed to not eat anything within 30 minutes of a sample, and may be asked to rinse their mouth with water after eating. The exact time of collection will be documented and the sample will be frozen at -20°C for later assay (if needed).

**Oral microbiome sample collection**. Studies have found that oral microbiota are impacted by delayed meal timing, which is common in shift workers and people obtaining insufficient sleep. Additional saliva samples and/or tongue swabs may be collected approximately once per day throughout the study for salivary/oral microbiome analysis. The exact time of collection will be documented and the sample will be frozen at -80°C for later assay.

**Genetic sample collection and whole genome sequencing**. Given the findings that genetic polymorphisms are associated with sleep, circadian, and metabolic physiology, we will collect genetic material from each participant for genome-wide analysis as well as future research. A total of 30mL of blood will be collected from each participant either at the time of discharge from the study or during a screening visit. Blood samples will be sent to the Mass General Brigham Biobank where DNA will be extracted, purified, and stored [49, 118, 119]. A portion of each sample may be sent to the Genomics Platform at the Broad Institute where standard whole genome sequencing (WGS) will be performed.

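### The 946 mL blood-draw maximum is not supported across the per-sample volumes the protocol permits: it can hold at low melatonin volumes but not at the upper stated one

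*Combined protocol and SAP*

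**What the plan says.** Section VII, under the common risks of blood sampling, gives a ceiling for the whole stay: "The total volume of blood drawn over the course of the month-long study will be no more than 2 pints (946 mL"). No derivation is shown.

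The draws are set out in Section V:

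- **Melatonin** (*Hormonal data*): "Samples of blood will be collected at approximately hourly intervals through the blood collection system described above". The volume is a range: "Blood samples (approximately 1-3mL) will be transferred to small (3 mL) vacutainer tubes and centrifuged". In the first baseline block sampling starts on the Day 6 morning, and "this sample collection will continue throughout the next three days (~Days 6-8"), ending about 10 hours after waking on the third day. The pattern recurs around Days 14-16, 23-25 and 31-33.
- **Meal tests** (*Standardized Mixed Meal Response test*): "Blood samples (approximately 4mL) will be collected using the sample collection system described above". Samples follow the meal every 10 minutes for 90 minutes, then every 30 minutes for 90 more. Pre-meal samples are in the plural, with no number.
- **IVGTT**: samples every 5 minutes over the 20 minutes before glucose, then "Blood samples will be taken at 2, 3, 4, 5, 6, 8, 10, 12, 14, 16, 19, 21, 22, 24" and onward to 180 minutes. No volume is given.
- **DNA** (*Genetic sample collection*): "A total of 30mL of blood will be collected from each participant", at discharge or at a screening visit. The paragraph on how biospecimens are obtained places it in screening.
- **Optional samples**: at the scheduled sampling times "we may collect additional small amounts of blood to assay for proteins, lipids, transcripts, or metabolites". The sleep-loss biomarker panel may also be drawn before each IVGTT. Neither has a volume.

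**The concern.** A limit worded as a maximum should hold at every volume the same protocol allows. Here one section fixes the total, another allows a threefold range for the most frequent draw, and the test with the most samples in a single session has no volume. Nothing adds these up.

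The ceiling is the protocol's safety statement on blood loss over the stay. If staff draw melatonin at the upper stated volume and follow the schedule, the statement would be wrong for that participant. If the ceiling governs, staff are not told which draws are to be smaller. As written, the ceiling cannot be verified from the document.

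**Working it through.** The plan's own figure cannot be rebuilt, since neither a derivation nor an IVGTT volume is given. Only the unit conversion can be checked: 2 US pints = 946.35 mL, which agrees.

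**Counts over four blocks**

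- Melatonin: waking on day one to 10 h after waking on day three = 24 + 24 + 10 = 58 h, so about 58 hourly draws per block and 4 × 58 = 232 in all. If 7 hourly draws per block coincide with the two tests and are shared (assumption), 4 × 51 = 204.
- Meal tests: 9 + 3 = 12 post-meal samples plus 2 pre-meal (assumption, the smallest plural) = 14. Volume: 4 × 14 × 4 mL = 224 mL.
- IVGTT: 31 listed times plus at least 4 before glucose = 35; 4 × 35 = 140. The IVGTT paragraph names only Days 7 and 15, but Aim 1 and the Section V schedule require a test before and after each intervention, hence four.
- DNA: 30 mL if it counts toward the stay, otherwise 0.

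**Volume used before any IVGTT sample, and room left**

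Low count = 204 × melatonin volume + 224 (draws shared, DNA at screening). High count = 232 × melatonin volume + 224 + 30 (no sharing, DNA counted). Room per IVGTT sample = (946 − volume used) / 140.

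| Melatonin per draw | Low count | Room per IVGTT sample | High count | Room per IVGTT sample |
|---|---|---|---|---|
| 3 mL | 612 + 224 = 836 mL | 110/140 = 0.8 mL | 696 + 254 = 950 mL | none (−4 mL) |
| 2 mL | 408 + 224 = 632 mL | 314/140 = 2.2 mL | 464 + 254 = 718 mL | 228/140 = 1.6 mL |
| 1 mL | 204 + 224 = 428 mL | 518/140 = 3.7 mL | 232 + 254 = 486 mL | 460/140 = 3.3 mL |

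**Totals at assumed IVGTT volumes, low to high count (140 samples)**

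| Melatonin per draw | IVGTT 1 mL | IVGTT 2 mL | IVGTT 3 mL | IVGTT 4 mL |
|---|---|---|---|---|
| 3 mL | 976-1,090 | 1,116-1,230 | 1,256-1,370 | 1,396-1,510 |
| 2 mL | 772-858 | 912-998 | 1,052-1,138 | 1,192-1,278 |
| 1 mL | 568-626 | 708-766 | 848-906 | 988-1,046 |

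At 3 mL melatonin every entry exceeds 946 mL. At 1 mL the total fits for IVGTT samples up to 3 mL. The 4 mL column is shown because the only stated volume for samples assayed for glucose and insulin is the meal test's 4 mL; the protocol does not say that the IVGTT uses it.

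**Sensitivity at 3 mL melatonin.** With one pre-meal sample instead of two, the low count is 612 + 208 = 820 mL, leaving 126/140 = 0.9 mL. With 48-hour blocks, one pre-meal sample, no DNA and no sharing, the volume used is 576 + 208 = 784 mL, leaving 162/140 = 1.2 mL; but 48 hours does not match the stated end of sampling.

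**The case against.** The strongest reply is that a ceiling and an approximate range are compatible: staff can draw toward the lower end, and the arithmetic confirms that this can work. The text also makes sharing natural. Melatonin is to be measured during the metabolic assessments, meal-test samples are kept for other hormones as well as glucose and insulin, and one collection system serves all draws. The optional samples may never be taken.

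Much of this stands, and it rules out several stronger readings that a reader might infer:

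- *That the ceiling is broken before any IVGTT sample.* The 950 mL figure exceeds it by 4 mL on approximate volumes. Without DNA it is 920 mL; with shared draws and DNA counted it is 612 + 254 = 866 mL.
- *That the schedule cannot fit, or fails over most of the range.* It fits at 1 mL melatonin with IVGTT samples up to about 3 mL, and at 2 mL for both it can fall either side (912 to 998 mL).
- *That samples late in the stay, in the second period, would be lost.* No passage says how the ceiling would be enforced.
- *That the accepted haemoglobin ranges contradict the anemia exclusion.* The protocol gives no haemoglobin threshold for anemia, and its screening table deliberately lists acceptable ranges wider than normal for most tests.

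What the reply does not answer is the upper end. Nothing tells staff to stay low, and 3 mL is a permitted volume. With sharing assumed and DNA left out, it leaves less than 1 mL per IVGTT sample.

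**Conclusion.** The concern holds in limited form. The 946 mL ceiling and the upper part of the stated melatonin range do not fit together once the IVGTT samples are counted. At 3 mL the room left is about 0.8 mL per IVGTT sample on the low count and none on the high count. At 2 mL the answer depends on an IVGTT volume that the protocol does not give, with break-even between about 1.6 and 2.2 mL. At 1 mL the ceiling can hold.

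This rests on about 58 draws per block, two pre-meal samples, 35 samples per IVGTT, four blocks, and the stated volumes taken at face value. Biomarker-panel, omics and safety-check samples are left out because they have no volumes; they can only raise the total. The point concerns a safety statement and its documentation. It is not evidence that the limit has been or will be exceeded, nor that any outcome is compromised.

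**What to change.** Reconcile the Section V schedule (both baselines, both interventions), *Hormonal data*, the meal-test, IVGTT and genetic-sample paragraphs, and the Section VII statement with one table of draw type, count and volume for all four blocks. The table should give the IVGTT volume and the number of pre-meal samples, say which hourly melatonin draws are shared with the tests, say whether the DNA sample counts toward the total, and include an allowance for the optional panel and omics samples.

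Then either bound the per-sample volumes so that the table's total stays inside the stated limit, or restate the limit wherever it appears. Which figure governs is for the sponsor's clinicians to decide. The cost is one small table and a wording amendment, with smaller sample volumes possible if the first route is taken. The statistical analysis need not change.
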